			+3		≥2/3 or ≥2/6 DLTs: +3 with further de-escalation: durvalumab 1500 mg + tremelimumab 75 mg + olaparib 200 mg			

*DLT – dose limiting toxicity in the first two cycles of treatment.

[figure not shown]
For further description of Table 1, please refer to Section 6.3..

Phase II (Dose determined after completion of the Phase I portion of the study):

Cohort	Dose Level	N	# of DLTs	Action Based on # of DLTs	Total #
Phase II Expansion cohort (2:1 ratio of platinum-resistant to platinum-sensitive)	durvalumab 1500 mg + tremelimumab 75 mg + olaparib 250 mg	27	N/A	N/A	18 platinum-resistant and 9 platinum-sensitive)

The study schema is depicted in Figure 1.

Figure 1 Study Schema

Enrollment into the study will be at a 2:1 ratio of platinum-resistant to platinum-sensitive disease only in the Phase II study. Enrollment into the safety lead-in cohort of the Phase I part will not be constrained to a 2:1 ratio of platinum-resistant to platinum-sensitive disease. Estimated total sample size including the Phase I lead-in and Phase II expansion cohorts, n = 33 to 39. It has been observed that ovarian cancer patients with BRCA1 and BRCA2 mutations tend to be more sensitive to platinum agents and possibly PARP inhibitors than wild-type BRCA ovarian cancers. In an initial proof-of-concept study of 50 BRCA1/BRCA2-mutated patients treated with 200 mg BID olaparib, objective response rates for platinum-sensitive and platinum-resistant cases were 46% and 33%. Therefore, in this combination drug therapy study, the Phase II study is planned to enroll at a 2:1 ratio of platinum-resistant to platinum-sensitive disease.

Durvalumab will be administered every 4 weeks (Q4W) for up to 1 year (13 cycles) and tremelimumab will be administered every 4 weeks (Q4W) for up to 4 doses/cycles. Olaparib will be administered 300 mg BID (or lower in the event of de-escalation) for up to 1 year. Study treatments will be continued for up to 1 year or until disease progression, whichever occurs sooner. Each cycle for durvalumab and tremelimumab is 4 weeks. Olaparib is continuous dosing. For the first 4 cycles (16 weeks), a patient will receive all three drugs and then continue with only

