6.2.1.2 Duration of Treatment and Criteria for Retreatment

For patients receiving durvalumab + tremelimumab + olaparib, retreatment is allowed (once only) for patients meeting the retreatment criteria below. The same treatment guidelines followed during the initial 12-month treatment period will be followed during the retreatment period, including the same dose and frequency of treatments and the same schedule of assessments. Similar to the initial treatment, in the event of disease progression while the patient is receiving durvalumab and olaparib alone (i.e. after completion of the first 4 doses of tremelimumab), the patient may be given an additional 4 doses of tremelimumab per the investigator's discretion, in combination with the ongoing durvalumab and olaparib.

Patients receiving the combination of durvalumab, tremelimumab, and olaparib may undergo retreatment in the clinical scenarios described below:

- Patients who achieve and maintain disease control (i.e., irCR, irPR, or irSD) through to the end of the 12-month treatment period may restart treatment with the combination upon evidence of PD according to irRECIST during follow-up.

- Before restarting their assigned treatment, the Investigator should ensure that the patient:
 - Does not have any significant, unacceptable, or irreversible toxicities that indicate continuing treatment will not further benefit the patient.
 - Still fulfills the eligibility criteria for this study, including re-consenting to restart durvalumab, tremelimumab, and olaparib.
 - Has not received an intervening systemic anticancer therapy after their assigned treatment discontinuation.
 - Has had a baseline tumor assessment within 28 days of restarting their assigned treatment; all further scans should occur with the same frequency as during the initial 12 months of treatment (relative to the date of randomization) until study treatment is stopped (maximum of 12 months of further treatment).

During the retreatment period, patients receiving durvalumab + tremelimumab + olaparib may resume durvalumab dosing at 1500 mg Q4W with 75 mg of tremelimumab Q4W for 4 doses each. Patients will then continue with durvalumab monotherapy at 1500 mg Q4W, beginning at Week 16, 4 weeks after the last dose of combination therapy (a total of 9 additional doses). Olaparib will be administered throughout this retreatment period at 300 mg BID (or the MTD in case of dose de-escalation) for up to 1 year.

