17. CT (preferred) or MRI scans, preferably with IV contrast, are collected during screening (for baseline), as close to and prior to initiation of study treatment. Timing of on-treatment CT/MRI scans is pre-dose C4D1 (± 7 days) for biopsy site determination and every 3 cycles thereafter (i.e. Day 1 of Cycles 7, 10, 13 ± 7 days) or as clinically indicated until progressive disease or off-study. Response according to irRECIST criteria (irCR, irPR) requires a confirmatory scan preferably at the next regularly scheduled imaging visit and no earlier than 6 weeks after the prior assessment of CR, PR, or SD is deemed by irRECIST. End of Treatment disease assessment does not need to be repeated if performed within 28 days prior to end of treatment.
18. Refer to Table 7 for details.
19. Refer to Appendix H and Appendix I for follow-up visits.
20. Results from CA-125 and thyroid function test do not need to be available prior to dosing patient on dosing days.

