	
(Colitis: abdominal pain; mucus or blood in stool) (Perforation: symptomatic; medical intervention indicated*)
 
* “medical intervention” is not invasive
	
 If toxicity improves to Grade ≤ 1, then study drug/study regimen can be resumed after completion of steroid taper. 	
(e.g., American Dietetic Association colitis diet), and loperamide and/or budesonide.
 
 Promptly start prednisone 1 to 2 mg/kg/day PO or IV equivalent. If event is not responsive within 3 to 5 days or worsens despite prednisone at 1 to 2 mg/kg/day PO or IV equivalent, GI consult should be obtained for consideration of further workup, such as imaging and/or colonoscopy, to confirm colitis and rule out perforation, and prompt treatment with IV methylprednisolone 2 to 4 mg/kg/day started. If still no improvement within 3 to 5 days despite 2 to 4 mg/kg IV methylprednisolone, promptly start immunosuppressives such as infliximab at 5 mg/kg once every 2 weeks a. Caution: it is important to rule out bowel perforation and refer to infliximab label for general guidance before using infliximab. Consider, as necessary, discussing with study physician if no resolution to Grade ≤ 1 in 3 to 4 days. Once the patient is improving, gradually taper steroids over ≥ 28 days and consider prophylactic antibiotics, antifungals, and anti-PJP treatment (refer to current NCCN guidelines for treatment of cancer-related infections).^a
	
Grade 3 or 4 (Grade 3: Diarrhea stool frequency of ≥ 7 over baseline per day; Grade 4 Diarrhea: life threatening consequences)
	
Permanently discontinue study drug/study regimen- for Grade 3 if toxicity does not improve to Grade < 1 within 14 days; study drug/study regimen can be resumed after completion of steroid taper.
 
Grade 4
	
For Grade 3 or 4:
 
 Promptly initiate empiric IV methylprednisolone 2 to 4 mg/kg/day or equivalent. Monitor stool frequency and volume and maintain hydration. Urgent GI consult and imaging and/or colonoscopy as appropriate.

Specific Immune-mediated Reactions			
Adverse Events	Severity Grade of the Event (NCI CTCAE version 4.03)	Dose Modifications	Toxicity Management

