Survival status: phone contact with subjects who refuse to return for evaluations and agree to be contacted		X	X	X	X	X	X	X (every 2 months)
Hematology ^c	X	X	X					
Chemistry ^d	X	X	X					
Thyroid function tests (TSH, and fT3 and fT4) ^e	X							

Evaluation	Time Since Last Dose of Durvalumab or Tremelimumab or Olaparib							
	Day (± 3)	Months (± 1 week)						12 Months and Every 6 Months (± 2 weeks)
	30	2	3	4	6	8	10	
Tumour assessment (CT or MRI)	
For subjects who achieve disease control following 12 months of treatment, tumour assessments should be performed every 12 weeks relative to the date of first infusion thereafter until confirmed PD by irRECIST by investigational site review. Please refer to Table 5 for timings of confirmatory scans.
 
For subjects who discontinue durvalumab + tremelimumab due to toxicity (or symptomatic deterioration), tumour assessments should be performed relative to the date of first infusion as follows: every 12 weeks until confirmed PD by irRECIST by investigational site review or started on standard therapy or another clinical study. Please refer to Table 5 for timings of confirmatory scans.
 
Upon confirmed PD or initiation of standard therapy, scans should be conducted according to local standard clinical practice.
							

- a Full physical exam (refer to Section 8.3.2).
- b Refer to Section 8.3.4.
- c Refer to Section 8.3.5, Table 6..
- d Refer to Section 8.3.5, Table 7.
- c Free T3 and free T4 will only be measured if TSH is abnormal. They should also be measured if there is clinical suspicion of an adverse event related to the endocrine system.

Appendix I Schedule of study procedures: follow-up for subjects who have discontinued study treatment due to confirmed progression of disease at the investigator discretion

Evaluation	Time Since Last Dose of Durvalumab or Tremelimumab or Olaparib						
	Day (± 3)	Months (± 1 week)					
	30	2	3	4	6	8	10
Physical examination ^a	X						
Vital signs (temperature, respiratory rate, blood pressure, pulse) ^b	X						
Weight	X						
AE/SAE assessment	X	X	X				
Concomitant medications	X						
Palliative radiotherapy	As clinically indicated						
ECOG performance status ^c	X					→	
Subsequent anti-cancer therapy	X	X	X	X	X	X	X
Survival status: phone contact with subjects who refuse to return for evaluations and agree to be contacted		X	X	X	X	X	X (every 2 months)
Hematology ^d	X						
Chemistry ^e	X						
Thyroid function tests (TSH, and fT3 and fT4) ^f	X						

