miRNA/mRNA (to examine immune cell gene expression profiles in circulation), if applicable	X						
blood for immune monitoring	X						
Tumour assessment (CT or MRI)	For subjects who continue on durvalumab + tremelimumab post-confirmed progression at the investigator's discretion (following consultation with the sponsor), tumour assessments should be performed relative to the date of first infusion per Table 5 until durvalumab + tremelimumab is stopped. For subjects who discontinue durvalumab + tremelimumab following confirmed progression , scans should be conducted according to local clinical practice and submitted for central review until a new treatment is started (these scans are optional).						

a Full physical exam (refer to Section 8.3.2)

b Refer to Section 8.3.4.

c Refer to Section 8.3.4, Table 6.

d Refer to Section 8.3.4, Table 7.

e PS to be collected if available at the 2 monthly calls to obtain subsequent anti-cancer therapy and survival status

f Free T3 and free T4 will only be measured if TSH is abnormal. They should also be measured if there is clinical suspicion of an adverse event related to the endocrine system.

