2.3 New Non-Measurable Lesions Definition and Assessment

- All new lesions not selected as new measurable lesions are considered new non-measurable lesions and are followed qualitatively.
- Only a massive and unequivocal progression of new non-measurable lesions leads to an overall assessment of irPD for the time-point.
- Persisting new non- measurable lesions prevent irCR.

2.4 irRECIST Overall Tumor Assessments

The irRECIST overall tumor assessment is based on the **TMTB** (total measured tumor burden) of measured target and new lesions, non-target lesion assessment and new non-measurable lesions.

Time point response assessments will be performed on Cycle 4 Day 1 (± 7 days) and then every 3 cycles.

Conventional RECIST 1.1 will also be documented during the trial however; RECIST 1.1 will not be used to determine disease progression. The irRECIST will be used for tumor response assessment at time of continuing review and will be used for IRB reporting and formal analysis.

- **irCR:** Complete disappearance of all measurable and non-measurable lesions. Lymph nodes must decrease to < 10 mm in short axis. Confirmation of response is not mandatory.
- **irPR:** Decrease of $\geq 30\%$ in TMTB relative to baseline, non-target lesions are irNN, and no unequivocal progression of new non-measurable lesions.
- **irSD:** Failure to meet criteria for irCR or irPR in the absence of irPD.

- **irNN:** No target disease was identified at baseline and at follow-up the patient fails to meet criteria for irCR or irPD.
- **irPD:** Minimum 20% increase and minimum 5 mm absolute increase in TMTB compared to nadir, or irPD for non-target or new non-measurable lesions. Confirmation of progression is recommended minimum 4 weeks after the first irPD assessment.
- **irNE:** Used in exceptional cases where insufficient data exists.
- **irND:** In adjuvant setting when no disease is detected.

New Lesions: the presence of new lesion(s) does not define progression. The measurements of the new lesion(s) are included in the sum of the measurements (the sum of the measurements = the sum of the longest diameters of all target lesions and new lesions, if any).

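### On-treatment scans follow antibody cycle days, and the plan does not say whether a held infusion moves the cycle; if it does, a Cycle 4 delay of 15 days or more puts the first scan after the 3-month landmark

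*Combined protocol and SAP*

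**What the plan says.** Table 5 footnote 17 (Section 8.2) sets the scan schedule: "Timing of on-treatment CT/MRI scans is pre-dose C4D1", plus or minus 7 days, then Day 1 of Cycles 7, 10 and 13, or as clinically indicated. Appendix K 2.4 repeats the anchor: "Time point response assessments will be performed on Cycle 4 Day 1". Section 4.1 defines the unit: "Each cycle for durvalumab and tremelimumab is 4 weeks".

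Appendix G governs holds of the antibodies. For Grade 2 diarrhea/colitis, once the event has improved to Grade 1 or less, "then study drug/study regimen can be resumed after completion of steroid taper". The management column beside it reads "Once the patient is improving, gradually taper steroids over ≥ 28 days and consider prophylactic antibiotics". Grade 2 pneumonitis and steroid-treated Grade 2 hepatic and renal events pair the same two conditions. Nothing says what happens to the cycle number during a hold.

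Calendar anchors do appear, but for other patients:

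- Appendix H, after stopping for toxicity: "tumour assessments should be performed relative to the date of first infusion as follows: every 12 weeks".
- Appendix I, treatment beyond confirmed progression: "tumour assessments should be performed relative to the date of first infusion per Table 5 until durvalumab + tremelimumab is stopped".
- Section 6.2.1.2, retreatment: "all further scans should occur with the same frequency as during the initial 12 months of treatment (relative to the date of randomization", although Section 8.1 describes enrollment as non-randomized.

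Section 12.4 tests 3-month PFS in the resistant stratum together with 6-month PFS in the sensitive stratum. It gives no time origin, no day count for a month, and no rule for a first scan that falls after the landmark.

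**The concern.** The primary test is a count of patients progression-free at two fixed times. It needs a disease assessment at or just before each time. With no delay, the Cycle 4 scan window closes on day 91, when three months are up, so there is almost no slack. If a hold carries Cycle 4 Day 1 along with it, the only scheduled scan before the landmark moves past it, and the patient's status at 3 months is not observed on schedule.

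The schedule can also behave oddly. A patient who stops the antibodies for toxicity is scanned 12 weeks from first infusion under Appendix H. A patient on a temporary hold, still on study treatment, could be scanned later than that. Sites that shift the cycle and sites that skip the dose would assess the primary endpoint at different times.

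**Working it through.** **The plan's own figure.** Inputs from Section 12.4: 18 resistant and 9 sensitive patients, null rates 0.55 and 0.65, alternatives 0.75 and 0.80, alpha 0.10. With fixed strata, R = Bin(18, p1) + Bin(9, p2).

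- Under the null, P(R ≥ 19) = 0.140 and P(R ≥ 20) = 0.068, so the cut-off is 20.
- At 0.75 and 0.80, P(R ≥ 20) = 0.717, which reproduces the stated 0.72.

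**Scan days.** Count days from first dose (assumed origin).

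- Cycle 4 Day 1 = 3 × 28 = 84, window 77 to 91. With a delay of d days the earliest allowed scan is 77 + d. It exceeds 91 (or 91.3) when d ≥ 15: 77 + 15 = 92. With 3 months taken as 89, 90 or 92 days, the limit is 13, 14 or 16.
- Cycle 7 Day 1 = 6 × 28 = 168, window 161 to 175. The earliest scan is 161 + d, which exceeds 182 (or 182.6) when d ≥ 22: 161 + 22 = 183.

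**Can Appendix G produce 15 days?** Hold length is not the same as cycle delay. Let onset be x days after an infusion (0 to 27), let the taper start t days later, and let it last the minimum 28 days. The earliest restart is x + t + 28 against a due day of 28, so the delay is x + t. The share of onset days with x + t ≥ 15 is (13 + t)/28:

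| t (assumed) | Share of onset days |
|---|---|
| 3 | 16/28 = 57% |
| 5 | 18/28 = 64% |
| 10 | 23/28 = 82% |

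These shares apply only to events treated with steroids and tapered over 28 days, with onset spread evenly over the cycle.

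**Effect on the primary test.** Suppose k of the 18 resistant patients have their first scan after the landmark. The cut-off stays at 20.

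- Progression dated to the late scan, none found earlier: every affected patient counts as progression-free. Type I error = P(k + Bin(18 − k, 0.55) + Bin(9, 0.65) ≥ 20).
- Half of these progressions found in time (assumed): affected patients succeed with probability 0.55 + 0.45 × 0.5 = 0.775.
- Affected patients scored as failures: power = P(Bin(18 − k, 0.75) + Bin(9, 0.80) ≥ 20).

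| k | Type I error, all progression-free | Type I error, half caught | Power, all failures |
|---|---|---|---|
| 0 | 0.068 | 0.068 | 0.717 |
| 1 | 0.091 | 0.080 | 0.598 |
| 2 | 0.121 | 0.093 | 0.460 |
| 3 | 0.159 | 0.108 | 0.318 |

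Under the failure rule with k = 2, type I error falls to 0.021.

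**The case against.** The documents lean toward a calendar reading. Appendix I speaks of first infusion and Table 5 in one breath, and the retreatment rule uses a fixed date. Section 4.1 equates four cycles with 16 weeks. Section 6.7 allows 13 doses within one year of first treatment: 13 × 28 = 364 days leaves no room for accumulated delays. If held infusions are skipped, scan dates do not move and the problem disappears. This makes the harmful reading less likely, but it does not settle the matter. Appendix I and the retreatment rule cover special cases, and the two places that schedule scans for a patient on treatment before progression use cycle days.

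A reader might infer that the gap favors the combination. The documents do not support that. The direction depends on a scoring rule that is not written, and one of the two obvious rules costs power instead.

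A reader might also infer that Appendix G always forces holds of four weeks or more. It does not. The taper length sits among management recommendations. Grade 2 hepatic and renal events get steroids only if they persist or worsen, Grade 2 rash is held only if persistent, and isolated hypothyroidism needs no interruption.

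Finally, the higher type I error figures are worst case. Footnote 17 permits clinically indicated scans, and a patient being worked up for colitis may be imaged anyway. Such scans are optional, however, so they soften the problem without closing it.

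**Conclusion.** The concern holds in conditional form. The on-treatment scan rule is tied to a cycle day whose behavior during a hold is undefined. If the cycle shifts, a Cycle 4 delay of 15 days, or a Cycle 7 delay of 22 days, puts the whole scan window past the landmark. That rests on a clock from first dose and 3 months of 91 days; other month conventions move the 15-day limit by one or two days.

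In the worst case one affected resistant patient keeps the type I error within 0.10 and two do not. If half the progressions are caught in time, it takes three. If affected patients are scored as failures, one already brings power below 0.60. How many would be affected is unknown: Section 1.3.2.3 reports diarrhea/colitis in 28.5% of the durvalumab plus tremelimumab pool, 5.8% at Grade 3 or higher, but gives no Grade 2 rate before week 12. The documents therefore do not show that the test is biased or its error rate inflated; they show that the result for such a patient hangs on two unwritten rules. The change lies between worth considering and advisable, mainly because it costs so little.

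**What to change.** In Table 5 footnote 17 and Appendix K 2.4, schedule on-treatment scans at weeks 12, 24, 36 and 48 (plus or minus 7 days) from first infusion, regardless of dose holds. Appendix H already uses this 12-week interval from first infusion. In Section 12.4, state that PFS is counted from first dose, with 3 months = 91 days and 6 months = 182 days. The landmark scans then fall on days 77 to 91 and 161 to 175, always on or before the landmark. Align footnote 16 so that the biopsy follows the week-12 scan.

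The cost is wording in four places. No patients are added and the design power stays at 0.717. For patients on hold, the scan and biopsy may fall outside a dosing visit. If the biopsy stays at a delayed Cycle 4 Day 1 instead, a repeat CT may be needed to choose the site. The change removes lateness caused by holds; it does not say how to score a scan that is simply missed.

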8.3 Description of Study Procedures

8.3.1 Medical history and physical examination, electrocardiogram, weight and vital signs

Findings from medical history (obtained at screening) and physical examination shall be given a baseline grade according to the procedure for AEs. Increases in severity of pre-existing conditions during the study will be considered AEs, with resolution occurring when the grade returns to the pre-study grade or below.

Physical examinations will be performed on study days noted in the Schedule of Assessments.

8.3.2 Physical Examination

Physical examinations will be performed according to the assessment schedule. Full physical examinations will include assessments of the head, eyes, ears, nose, and throat and the respiratory, cardiovascular, GI, urogenital, musculoskeletal, neurological, dermatological, hematologic/lymphatic, and endocrine systems. Height will be measured at Screening only. Targeted physical examinations are to be utilized by the Investigator on the basis of clinical observations and symptomatology. Situations in which physical examination results should be reported as AEs are described in Section 10.

8.3.3 Electrocardiograms

Resting 12-lead ECGs will be recorded at screening, on Cycle 1 Day1 within 2-3 hours prior to the start of the first study treatment and 0-3hrs after administration of the combination is completed, on Cycle 5 day 1 OR at least one time after starting study treatment and as clinically indicated throughout the study. ECGs should be obtained after the patient has been in a supine position for 5 minutes and recorded while the patient remains in that position.

At Screening, triplicate ECGs (2-5 minutes apart) will be obtained on which QTcF must be <470 ms.

For all other time points, a single ECG will be performed. In case of clinically significant ECG abnormalities, including a QTcF value ≥ 470 ms, 2 additional 12-lead ECGs should be obtained over a brief period (e.g., 30 minutes) to confirm the finding.

Situations in which ECG results should be reported as AEs are described in Section 10.

